Cover Page

**Official title: „Randomised cross-over Study
on the Effectiveness of Elaboration and
Proactive Feedback as Part of Formative Key
Feature Examinations in Undergraduate
Medical Education“**

NCT number: not yet assigned

Document date: 28/8/2018

Trial Protocol

Title:

„Randomised cross-over Study
on the Effectiveness of Elaboration and
Proactive Feedback as Part of Formative Key
Feature Examinations in Undergraduate
Medical Education“

Project Lead:
[name]. med. [name]
Division of Medical Education Research and Curriculum Development
University Medical Centre Göttingen

There is no third-party funding or support for this trial.

1. Study aim

Repeated formative (i.e., non-graded) testing enhances student learning outcome on clinical reasoning skills. At University Medical Centre Göttingen (UMG), a number of trials investigating the so-called *testing effect* have already been conducted in the past. They showed, amongst others, that dealing with videotaped clinical cases compared with written cases increases short-term outcome but not long-term retention. More recently, one study addressed the question whether clinical reasoning skills can be fostered by an elaboration of incorrect answers. Results of a previous trial had suggested that a considerable number of students were not sufficiently motivated to provide thorough answers to elaboration questions. This impression remained even after introducing financial incentives for students although a small but significant effect of the intervention was noted (percent score in the exit exam: $65.7 \pm 19.6\%$ vs. $62.3 \pm 22.9\%$; $p = 0.022$). Yet, student performance remained moderate at best. Thus, the intervention will now be extended by including automated feedback provided by email. All students participating in an electronic case-based seminar (e-seminar) will receive an individual email after the event, displaying their raw point score as well as their written answers to elaboration questions and expert comments reflecting current medical knowledge.

This trial addresses the following research question:

What is the effect of elaboration and consecutive automated and individual feedback following e-seminars on medical students' clinical reasoning skills?

2. Background and previous work

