Current findings from educational psychology research suggest that diagnostic errors made in a protected learning environment can serve as starting points for further elaboration which may eventually lead to a reduction in diagnostic errors in clinical practice. This trial aims to implement and evaluate this concept. To this end, existing data obtained in previous trials at UMG were analysed with regard to common clinical reasoning errors (CCRE). On this basis, e-seminars running in parallel to curricular teaching in the three aforementioned modules were modified in that – upon answering specific questions – students were prompted to comment on frequent CCREs ('elaboration'). The analyses of student entries revealed that despite all the content having been covered in preceding teaching sessions, a considerable proportion of entries represented slack answers (e.g., 'don't know' or 'no idea'), suggesting that students might not have taken the exercise serious enough. In fact, this notion was corroborated in student comments during focus group discussions following the main study. As a consequence, the study was repeated in the following year, and this time complete answers to elaborations questions were incentivised using book vouchers. In this setting, a significant effect of the intervention was noted but student performance was still at best moderate. Given the importance of feedback for learning processes elicited by formative examinations, this aspect will be strengthened in the trial described here. Students can already open a text box containing static feedback after each question, but so far they have not received personal feedback after each exam. In winter term 2018/19, all students participating in the trial will receive individual emails containing (a) the raw point score achieved in each e-seminar, (b) static expert feedback to elaboration questions, and (c) their own entries to these elaboration questions. Thus, students will be able to compare their own answers to the instructor feedback.

3. Design and Conduct of the Study

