This is a randomised controlled cross-over educational trial. Participating students will be stratified according to sex and summative exam scores in the previous term. Subsequently, they will be randomized to one of two study groups in a 1:1 fashion. During weekly e-seminars, they work on clinical cases addressing diagnostic and therapeutic strategies needed to manage patients with prevalent symptoms of general medical disorders. Cases will be presented as key feature cases with five questions per case. For some of these questions, elaboration questions will be written. These will focus on common misperceptions and clinical reasoning errors. When used as 'intervention items', elaboration questions will be shown after the original key feature question. Students will be prompted to enter a free-text answer. Upon completing both the original item and the elaboration question, they will be able to access a static feedback ('expert comment'). This feedback will be included in an email sent to all students on the day after the e-seminar, also containing individual performance data as well as the student's free-text answer to the elaboration question. When used as a 'control item', the same key feature question is being displayed, and students can access the expert comment directly after answering the question. Information on control items will not be contained in the mailed feedback. Every student will be exposed to 15 intervention and control items, respectively, and each of these will be shown twice over the course of 10 weeks. Items that are being shown as intervention items in one randomized group will be shown as control items in the other group and vice versa, thus making each student their own control. At the end of the study, individual 'intervention item' and 'control item' scores will be computed for each student, and these two scores will be compared using a paired t Test. This primary analysis will be done to test the following hypothesis:

„Long-term retention will be better for content that has been repeatedly tested with additional elaboration questions and subsequent mailed individual feedback than for content that has been repeatedly tested alone.“

Long-term retention will be assessed in a formative electronic key feature assessment in summer term 2019. It will be identical to the entry and exit exam held in winter term 2018/19.

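### Does the paired t test on per-student scores need replacing or supplementing because it ignores item-to-item variation in the effect?

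*Protocol*

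**What the plan says.** Section 3 (Design and Conduct of the Study) sets out the design and the primary test:

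- Items: "Every student will be exposed to 15 intervention and control items, respectively". An item that is an intervention item in one randomised group is a control item in the other, so 30 items are used in all.
- Scores and test: "individual 'intervention item' and 'control item' scores will be computed for each student", and "these two scores will be compared using a paired t Test".
- Hypothesis: "Long-term retention will be better for content that has been repeatedly tested with additional elaboration questions", together with the emailed feedback, compared with content that was tested repeatedly without them.
- Outcome: a formative key feature exam in summer term 2019. "It will be identical to the entry and exit exam held in winter term 2018/19".
- Structure of the material: "Cases will be presented as key feature cases with five questions per case".

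Section 1 (Study aim) puts the research question more broadly: "What is the effect of elaboration and consecutive automated and individual feedback following e-seminars on medical students' clinical reasoning skills"? Neither the primary analysis nor the secondary regressions described at the end of Section 3 names an item or case term.

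**The concern.** Collapsing 30 items into two scores per student leaves only variation between students in the standard error. If the benefit of elaboration differs from item to item, the average over these 30 items is itself a draw from a wider range of possible item sets. That draw is the same for every student, so adding students does not average it out. A result presented as a finding about clinical reasoning skills, the term used in Section 1, would then carry too small a standard error, and the shortfall would grow with the size of the trial.

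The effect expected here may be small. Section 1 reports 65.7% against 62.3% (p = 0.022) for a related intervention, so a modest amount of extra variance could decide whether a general claim is supported.

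**Working it through.** The protocol gives no sample size, power or significance level, so there is no design figure to reproduce. The check has three parts.

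**1. What the paired t test estimates.** In one group a student's difference is the mean effect on set 1 plus the difficulty gap between sets. In the other it is the mean effect on set 2 minus the same gap. With equal groups the gap cancels, and the mean difference is the average effect over the 30 items.

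This was simulated with 4,000 runs per setting: two swapped sets of 15 items, equal groups, and an assumed residual SD of 40 points per item. N ran from 60 to 200 and the between-item SD of the effect, w, from 0 to 15 points. The error rate for the 30-item average was:

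- 4.1% to 5.4% with equally difficult items
- 3.0% to 3.9% with an assumed item-difficulty SD of 20 points. Here the test is conservative, because the gap between sets inflates the SD of the paired differences.

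**2. What it omits for a wider claim.** The standard error for a claim about a population of similar items is

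SE_wide = √(SE² + w²/30).

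The only usable effect in the document is the related trial's: 65.7 − 62.3 = 3.4 points with p = 0.022. Assuming a two-sided paired test and a normal reference, SE = 3.4 / 2.29 = 1.48. Thirty items are assumed for that trial too.

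| w (points, assumed) | w/√30 | SE_wide | p for 3.4 points |
|---|---|---|---|
| 0 | 0 | 1.48 | 0.022 |
| 5 | 0.91 | 1.74 | 0.051 |
| 7.5 | 1.37 | 2.02 | 0.09 |
| 10 | 1.83 | 2.35 | 0.15 |

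In the same simulation, the error rate of the paired t test for the wider claim (equally difficult items) was:

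| N (assumed) | w = 0 | w = 5 | w = 10 |
|---|---|---|---|
| 60 | 5.4% | 7.5% | 15.0% |
| 100 | 5.0% | 9.2% | 21.2% |
| 200 | 5.1% | 14.0% | 32.8% |

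The figures move with the assumptions. With an item-difficulty SD of 20 the row for N = 100 becomes 3.6%, 6.8% and 17.8%. A second simulation with right/wrong items (mean 64%, item-difficulty SD 18, student SD 15) gave 4.0%, 7.2% and 15.6%. Effects correlated within a case would raise them. With three study items per case and an intraclass correlation of 0.5 (both assumed), the omitted variance is multiplied by 1 + 2 × 0.5 = 2, and the simulated error at N = 100 was about 10% at w = 5 and 25% at w = 10.

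**3. Which claim the plan makes.** The hypothesis compares material already tested in two ways, which most naturally means the study items. The outcome exam repeats the entry and exit exam, and no new or transfer items are described. Hypothesis, outcome and test therefore share one target: the average effect on the tested content. Part 1 shows the test is sound for it. Part 2 applies only to a claim that the protocol does not set out to test.

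**The case for a change.** The strongest case for a change is that Section 1 asks about clinical reasoning skills and cannot be read as a question about 30 items. The protocol neither limits its conclusion nor names an analysis that would support a wider one. One sentence on scope and one prespecified item-level mixed model would cost little and need no new data.

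Part of this stands. A statement about clinical reasoning at large would go beyond what the paired t test shows, and the omitted variance is real whenever w is above zero. The rest does not lead to a change:

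- Section 1 gives the motivating question; Section 3 turns it into the hypothesis that is tested. Exam-based trials routinely make this step from construct to items.
- The elaboration questions were aimed at common reasoning errors, so the items were not randomly sampled. The term w²/30 then has no firm sampling basis. A mixed model would support a claim about similar items at most, and not about reasoning measured in other ways.
- A supportive model is commonly left to the SAP, which is not at hand.
- The model has costs. A logistic form presumes right/wrong scoring, which the protocol does not state, and it changes the effect scale from a difference in mean scores to log-odds. Convergence with random slopes for both students and items is not assured.
- The remark in Section 2 that "a considerable proportion of entries represented slack answers" concerns entries in a previous study. It does not show how far the effect varies between students or items.

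**Conclusion.** No change follows. Treating the items as fixed is a legitimate choice, and the planned test answers the Section 3 hypothesis for the average effect on the 30 items. This rests on near-equal group sizes among students who sit the retention exam. A 55/45 split with an assumed 10-point gap in set difficulty would shift the estimate by (0.55 − 0.45) × 10 = 1.0 point. With an item-difficulty SD of 20 and N = 100, the simulated error was 5.4% at 55/45 and 10.8% at 60/40. Randomisation is 1:1, so a marked imbalance would have to come from dropout.

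For a wider population of items the shortfall runs from nothing (w = 0) to an error of about 21% at w = 10 and N = 100, and about 33% at N = 200. Both w and N are assumptions, so the size cannot be fixed from the document. The practical consequence is one of reporting: the primary conclusion belongs to the content tested. Authors wanting to speak about similar items could add a supportive item-level model on a scale that fits the scoring, but the plan is sound without it.

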Secondary analyses will include unadjusted and adjusted linear regressions with percent scores in the exit exam and retention test as dependent variables and student characteristics as well as their engagement with key feature questions as independent variables.

4. Enrolment

Before the beginning of winter term 2018/19, all students enrolled to the three modules will receive an email describing the study. Particular emphasis will be put on the fact that study participation is voluntary. Students will be invited to participate in the trial. In this context, participation means that students agree to having their data analysed for the purpose of the trial. Every student will receive teaching and will also be invited to take e-seminars regardless of study participation. Written consent will be obtained in a classroom session on the first day of the module.

5. Archiving and Data Protection

For communication purposes, student names and email addresses need to be known. For each student providing written consent, these data as well as exam scores achieved in the preceding term will be provided by the Study Deanery. Personal data will be stored on a desktop computer to which only the Project Lead has access.

During e-seminars, students log onto the system using their individual credentials. Output files of the key feature examination system contain student login names. These will be used to merge files from various sources. Following the merging procedure and before running any analyses, all personal data will be deleted from the dataset. As a consequence, no individual student can be identified in this final dataset.

Responsibility for data treatment and storage lies with the Project Lead.

The Trial Protocol as well as all related documents have been approved by the institution's data protection officer, [name].

Participating students are entitled to seek information on which of their personal data are being stored, and they can request all data to be deleted as long as they can still be identified in the dataset.

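### Does the plan need a stated treatment comparison for the exit exam, given that the secondary regressions contain no intervention term?

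*Protocol*

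**What the plan says.** Section 3 of the protocol describes a design in which each student meets 15 intervention items and 15 control items, with the item sets swapped between the two randomised groups. A score for each item type is computed per student, and "these two scores will be compared using a paired t Test". The hypothesis attached to this test concerns retention, and "Long-term retention will be assessed in a formative electronic key feature assessment in summer term 2019". The retention test has the same content as the entry and exit exams of winter term 2018/19.

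The last paragraph of section 3 says that the secondary analyses will include "unadjusted and adjusted linear regressions with percent scores in the exit exam and retention test as dependent variables". The predictors are "student characteristics as well as their engagement with key feature questions as independent variables". The paragraph does not say whether the percent score covers all items or one item type.

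Section 1 (Study aim) gives the result of the earlier elaboration trial as a "percent score in the exit exam" of 65.7 ± 19.6% against 62.3 ± 22.9%, p = 0.022. It also says of a different comparison, videotaped against written cases, that the former "increases short-term outcome but not long-term retention".

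**The concern.** Two things catch the eye. First, the secondary regressions list neither item condition nor randomised group, so they cannot say anything about the intervention. Second, the exit exam appears only as an outcome of these regressions and as the twin of the retention test, so the document states no treatment comparison for it.

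At stake is the interpretation of the retention result. If retention shows no difference, a reader would want to know whether there was never a gain or whether an early gain faded. A reader would also want a figure to set beside the 3.4-point exit-exam difference that motivates the trial. A further worry is that engagement is chosen by the student, so its coefficient may reflect ability rather than any effect of engaging.

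**Working it through.** The protocol gives no figure for this point that could be reproduced. The check is structural, with arithmetic where it helps.

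**1. Where the treatment effect goes in the listed regressions.** Let *d* be the effect on an intervention item. Every student has the same 15/15 split (section 3), so

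total score = (intervention score + control score)/2 = ability + *d*/2 + error.

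The term *d*/2 is the same for everyone and enters the intercept. One simulated data set illustrates this. Its assumptions, which are not in the protocol, are 120 students, one item set 4 points harder than the other, and sex, prior score and engagement as predictors. The same random draws were used for each *d*.

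| True effect *d* | Intercept | Sex | Prior score | Engagement | Mean intervention-minus-control difference |
|---|---|---|---|---|---|
| 0 | 59.71 | 1.2793 | 5.8283 | 3.6086 | -1.34 |
| 3.4 | 61.41 | 1.2793 | 5.8283 | 3.6086 | 2.06 |
| 10 | 64.71 | 1.2793 | 5.8283 | 3.6086 | 8.66 |

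The intercept rises by 1.70 = 3.4/2 and by 5.00 = 10/2, and no slope moves. Adding randomised group does not help: its coefficient is -2.8079 in all three rows. With the intervention-item score alone as the outcome, again only the intercept moves (59.33, 62.73, 69.33). The within-student difference rises by exactly *d*; its value of -1.34 at *d* = 0 is sampling noise.

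The regressions therefore carry no treatment contrast under either reading of the percent score. The within-student comparison, which is the stated primary method, does carry it.

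**2. Which exam the paired test uses.** The sentence introducing the test places it at the end of the study without naming an exam. The hypothesis and the sentence after it both point to the summer 2019 test. On the text, the exit exam has no stated treatment comparison.

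**3. What the earlier figure amounts to.** The difference is 65.7 - 62.3 = 3.4 points. If that test was paired and two-sided, SE = 3.4 / t(0.989, n - 1). This gives 1.445 for n = 60 and 1.477 for n = 300, hence a 95% confidence interval of about 0.5 to 6.3 points in either case. This describes the earlier trial only. It does not measure any loss in the present one.

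**4. What would be needed to obtain the exit-exam contrast.** The exit exam is planned, has the same content as the retention test, and can be scored by item type in the same way. The identical paired comparison can be run on it. No design change and no extra data are required.

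**5. The engagement coefficient.** Assume 100 students, an ability-score correlation of 0.6 and no effect of engagement itself. The simulated rate of significant engagement coefficients is then 5% when engagement and ability are uncorrelated. It is 22% to 86% unadjusted when they correlate at 0.2 to 0.5. Adjusting for the previous-term score lowers this to between 6% and 68%, depending on how well that score tracks ability. None of these correlations is in the protocol, so the range says only that confounding is possible.

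**The case for a change.** The strongest case for a change is that the protocol does more than stay silent: it names the outcomes and predictors of its secondary models, and the treatment is not among them. The exit-exam difference is the trial's own motivating result, and a comparison chosen after the data are seen carries less weight than one named beforehand. A regression of the within-student difference would also show whether benefit depends on engagement, which matters because section 2 reports slack answers in the earlier work.

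Part of this stands. The exit-exam comparison is not written down, and stating it in advance has some value. The rest is weaker.

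- The regressions are not presented as treatment-effect analyses. As descriptions of who performs well they are legitimate, and an association that arises through ability is still a real association in such a model. The protocol makes no causal claim about engagement. Adjusted models are already planned, and "exam scores achieved in the preceding term will be provided by the Study Deanery", so the obvious covariate is at hand.
- The evidence that early gains can fade comes from videotaped against written cases. The protocol reports no fading for elaboration, so the argument is by analogy.
- Difference-score regression answers a different question and has its own costs. Under the assumptions of step 5 its standard error is 1.7 against 1.3 points per SD of engagement. It still rejects 9% to 23% of the time when benefit correlates at 0.2 to 0.3 with ability (engagement-ability correlation 0.3 to 0.4).

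**Conclusion.** The observation is accurate, but it describes unstated detail, not an error. Followed as written, the plan yields its within-student primary comparison on retention and descriptive regressions that claim nothing about the intervention. The list of secondary analyses is open-ended. A paired exit-exam comparison, the definition of the percent score and the choice of covariates are matters commonly settled in a statistical analysis plan, which may exist and was not available. The earlier trial was reported with exactly this exit-exam contrast, so an analyst would have little doubt how to produce it.

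The primary result is not affected, and no sample size or power figure in the protocol depends on this point. The conclusion assumes that the exit exam is scored by item type in the same way as the retention test, which its identical content makes natural. It also assumes that the regressions are reported as predictors of performance and not as evidence for the intervention.
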